Some infants with other seriously life-threatening illnesses may not be diagnosed in the early hours and days. This is because some conditions require expensive or invasive diagnostic tests, and others, such as sepsis, may be undetectable for a period of time. If these infants meet all other criteria, then they would be enrolled in the prospective cohort even though they are at higher risk of mortality. Most of these cases will die before 72 hours, since neonatal mortality is concentrated early. In those cases we will replace the infant in the cohort sample. (See section below on “replacement of infants who die in the first 72 hours.”)

Plans to leave the study area before end of data collection

In order to conduct the study, we will need to be able to follow mother-infant pairs. If a mother-infant pair plans to leave the study area within 6 months, per maternal self-report, they will not be enrolled. As part of the study set up, we will seek additional insight from local partners on practices of returning to maternal home for birth of child.

Young mother

In Tanzania and India, women under 18 will be excluded.

In Malawi, women aged 16 to 17 who are married are considered legally emancipated and able to give independent consent, so they may participate. Women who are 16 to 17 and are unmarried will be excluded. All women and girls under 16 will be excluded.

Maternal death

The study will exclude cases of maternal death that occur during labor and delivery (or at any time before the consenting process would begin for this study.) Although the LBW infants of deceased mothers are particularly vulnerable and important to study, we anticipate very few, if any, maternal deaths in samples of roughly 300 in each site. Also, given the logistical and ethical complexity in recruiting and following these cases, they would likely require separate study processes, which would take effort and scarce study resources to prepare for, even if no deaths occur.

Maternal deaths will count as an exclusion criteria for the prospective cohort if they occur before enrollment. In the event that a mother dies at any time after enrollment, the infant will still be retained in the cohort.

Infant death

The study will exclude infants that die before enrollment can occur, as well as infants that are part of multiple births where the other baby(ies) have died (even if the surviving infant is otherwise eligible).

Infant >72 hours old at screening

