Infants must be enrolled in the prospective cohort study within 72 hours of birth. If the infant is older than 72 hours at the time of screening, s/he will be ineligible for the study.

Mother-infant pairs with the following traits will still be eligible for the study, given that no exclusion criteria are met.

Gestational age

As birthweight will be the main criteria for eligibility, we will enroll infants of any gestational age, as long as they meet the other inclusion criteria.

Multiples

Twins or triplets will be considered for enrollment in the study as multiples have higher rates of LBW and greater demands on a lactating woman. For the extension, they will still be considered as long as they are in the current prospective cohort. If only one infant in a multiple birth qualifies for inclusion, that infant may be enrolled and followed as a singleton would. If both infants qualify, both may be enrolled.

Maternal HIV Status

Women who are HIV infected are eligible. We will encourage the adherence to Option B+ standards so women are receiving HIV antiretroviral therapy in concordance with WHO and national guidelines.

Language

Mothers who do not speak English will still be eligible for the study.

Out-of-facility birth

Infants may be born anywhere and still be eligible for the study, as long as they present at a study facility for weight measurement within 72 hours of birth. See details below on identification and recruitment of these infants.

Prospective Cohort Extension study: This component will consist of enrolling mother/infant pairs.

Inclusion criteria for the mother/infant pair are:

- Currently enrolled in the LIFE study (follow-up from birth to 6 months of age) and fulfills all original inclusion criteria (infant birthweight between 1500g and <2500g, residence in catchment area of facilities in which born)
- Mother's and/or legally accepted representative (surrogate's) consent obtained for herself and infant for another 6 months of follow up

Exclusion criteria for the mother/infant pair are:

- Not previously enrolled in the LIFE study in addition to all original exclusion criteria (birthweight outside range, congenital abnormalities at birth, neonatal encephalopathy at birth, young mother, maternal death during labor and delivery, infant death before 72 hours of life, infant is more than 72 hours old at enrollment)

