9.5 Replacement of infants who die in the first 72 hours

As described in the exclusion criteria for the prospective cohort, it will not be possible to identify all infants with severe or critical illness before discharge. Because not all diagnoses can be made definitively before discharge, some critically ill infants may end up in the prospective cohort, and may, unfortunately, die early.

These cases will not contribute much data to the study on their growth and feeding patterns, and may erode our ability to achieve our target sample size. We aim for 350 mothers at enrollment with 300 still

enrolled at 6 months. The drop of 50 mothers is due to expected loss to follow up as well as deaths. However, this margin may not be large enough to cover all the deaths if we include infants who have serious illnesses that are not apparent at discharge. In that case, we may end up with more infants than expected dying in the first few days, and fewer than 300 infants by six months.

For these reasons, we will consider an enrolled infant who dies within the first 72 hours to be excluded from the cohort, and we will recruit an additional infant in its place. In effect, this puts an additional inclusion criterion on this cohort, which is surviving the first 72 hours of life. If the infant dies at any time after 72 hours, he or she will not be replaced in the sample.

Baseline data from infants who die in the first 72 hours will not be included in the formal analyses, but may be included in post-hoc explorations.

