9.6 Assessment of congenital abnormalities and serious illnesses in infants

Some of the congenital abnormalities and serious illnesses will be readily apparent at birth, such as cleft lip. However, at first screening, it may not be possible for the clinicians to conclusively state whether the infant has some of the other congenital abnormalities or serious illnesses in our exclusion criteria. Some conditions may take a day or several days to fully develop.

[figure not shown]
Figure 2 shows how cases will be handled. Infants who clearly have the condition or illness at the first screening will be ineligible, and if they clearly do not, they will be eligible. In the event that it is unclear, then the study staff will revisit the mother-infant pair several hours later, the amount of time depending on the clinical judgment of the facility staff. If at that repeat screening the infant's condition is still not clear, study staff will again delay screening and revisit later.

In the end, the final screening will take place when the infant is discharged or when 72 hours has elapsed since birth, whichever comes first. In either case, as shown in Figure 3, if the condition is still unclear, then the infant will be treated as eligible. If the infant is enrolled at discharge before 72 hours, and then happens to die within the 72 hour mark, that infant will be replaced in the prospective sample. If the infant is enrolled at 72 hours, it will be kept in the prospective sample even if it dies soon afterward.

Figure 2. Screening for infant conditions

Screening for infant conditions

Congenital conditions that interfere with feeding
Critical or serious illnesses that jeopardize survival to 72 hours

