9.18.6 Infant health questionnaire

Information on infant health will be captured through a questionnaire to the mother or primary caregiver (i.e. self-report from mother/caregiver), and clinical records (when available). The infant health questionnaire will include the topics below. We will also pilot infant morbidity in-home diaries for mothers to record daily details on selected morbidities like diarrhea, vomiting and respiratory infections) that are most likely to influence infant feeding and growth. Diaries will be introduced at the Week 6 visit (when transitioning to monthly follow-up visits), and mothers will be instructed to fill the diaries to use as a recall aid for subsequent visits. An extended list of questions will be asked at 9 and 12 months and a short list may be asked during the phone calls.

Infant severe morbidities and need for clinical care

- *Diarrheal disease*
Including history of:
 - Persistent diarrhea (diarrhea that lasts for >14 days, often seen in infants who are malnourished)
 - Acute diarrhea (diarrhea lasting 14 days or less)
 - Severe diarrhea: diarrhea that is associated with signs of clinical dehydration including sunken eyes, lack of thirst, tenting with skin pinch, etc
 - Hospitalizations for diarrheal illnesses (Bhandari 2003)
- *Pneumonia/acute respiratory infection* - possible though maternal self-report and clinic records. Definition: cough or difficulty breathing plus either fast breathing or chest wall indrawing (WHO 2013).
- *Sepsis or other severe infection*

- Possible serious bacterial infection in a young infant: evidence of severe clinical illness in an infant aged 7-59 days per IMCI criteria
- Very severe febrile illness: Fever + danger signs in a child 60 days or older per IMCI criteria
- Positive blood culture or CSF culture at any age. This will be documented based upon maternal self-report, patient personal health records, or clinic record.
- *Malaria*, diagnosed by rapid test or parasitological confirmation will be documented based upon maternal self-report, patient personal health records, or clinic record.
- *Necrotizing Enterocolitis (NEC)*: Definitions (based on clinic records and maternal report):

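### The listed sepsis items have no clinical criterion before day 7, so a first-week episode without a positive culture that ends before day 7 is not classified as sepsis

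*Combined protocol and SAP*

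**What the plan says.** Section 9.18.6 lists three items under sepsis or other severe infection:

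- a clinical item for the young infant, possible serious bacterial infection, which is described as "evidence of severe clinical illness in an infant aged 7-59 days per IMCI criteria";
- a second clinical item that takes over at later ages and is worded "Very severe febrile illness: Fever + danger signs in a child 60 days or older per IMCI criteria";
- a laboratory item without any age floor, given as "Positive blood culture or CSF culture at any age".

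The information comes from the mother's or caregiver's report "and clinical records (when available").

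The first week is inside the observed period. Section 9.1 states: "Infants must be enrolled in the prospective cohort study within 72 hours of birth". Table 7 in section 9.14 schedules the infant health questionnaire at baseline and at week 1.

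The plan also expects early sepsis in the cohort. Section 9.1 says that some life-threatening conditions will not be diagnosed at enrolment because they need expensive or invasive tests, while "others, such as sepsis, may be undetectable for a period of time". Such infants are enrolled if otherwise eligible. The plan expects most of them to die before 72 hours and be replaced. After that point, section 9.5 says "If the infant dies at any time after 72 hours, he or she will not be replaced in the sample", and section 9.6 says "If the infant is enrolled at 72 hours, it will be kept in the prospective sample even if it dies soon afterward".

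Section 9.12 makes point estimates and confidence intervals for the percentages of infants with particular conditions the main statistical results. It names any sepsis among three outcomes that matter to LIFE when it takes twin correlations from the literature.

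**The concern.** Both clinical items carry an age floor, and the lower one is day 7. For the first seven days of life the listed items leave culture as the only route to a sepsis classification. No section gives a clinical criterion for those days or a reason for starting at day 7. The neighbouring definitions of pneumonia and suspected NEC rest on clinical signs and have no age floor.

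At stake is the meaning of a descriptive morbidity result under Objective 2. The plan does not say which ages its sepsis percentage covers. If a table presents that percentage for the whole follow-up, first-week episodes without a positive culture are in the denominator's time at risk but cannot enter the numerator. The shortfall runs one way relative to clinical-or-culture sepsis, and a larger sample does not reduce it. The extension analyses in section 9.20 describe morbidity over time and model its contribution to growth, so a definition that changes at day 7 would carry into them.

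**Working it through.** **Coverage by age.** Taking the three items in section 9.18.6 day by day:

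| Age | Clinical item | Culture item |
|---|---|---|
| Days 0 to 6 | none | yes |
| Days 7 to 59 | yes | yes |
| Day 60 onward | yes | yes |

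The two clinical items leave no gap from day 7 onward. The uncovered days are exactly 0 to 6. An infant still ill on day 7 can meet the 7 to 59 day item, so the gap is limited to episodes that end before then. It includes episodes in which no culture was taken.

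**Who is affected.** Infants who die within 72 hours are excluded and replaced (section 9.5). Among deaths, the gap therefore matters from 72 hours to day 6. Among survivors it covers all of days 0 to 6.

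**The plan's own precision figure.** Half-width = 1.96 × √(p(1−p)/n). With n = 250 and p = 0.05 (section 9.12), 1.96 × √(0.05 × 0.95/250) = 0.027. The interval is 2.3% to 7.7%, as the plan states.

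**Inputs for size.** I use n = 300 per site, the target number of mothers. Section 9.12 expects slightly more infants (304 to 313), which changes little. The 5% is that section's generic worked example, not a sepsis rate. The 10% is my assumption. Let f be the share of all cases that lack a positive culture and end before day 7. The documents give no value for f, so I show an assumed range of 10% to 50%.

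**Reported percentage** = p × (1 − f):

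| True p | f = 10% | f = 25% | f = 50% |
|---|---|---|---|
| 5% | 4.5% | 3.75% | 2.5% |
| 10% | 9.0% | 7.5% | 5.0% |

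Each missed infant lowers a site's percentage by 1/300 = 0.33 points.

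**Comparison with sampling error at n = 300:**

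- p = 0.05: half-width 0.0247; 0.0247 × 300 = 7.4, so 8 of 15 cases would have to be missed; break-even f = 0.0247/0.05 = 0.49.
- p = 0.10: half-width 0.0339; 0.0339 × 300 = 10.2, so 11 of 30 cases would have to be missed; break-even f = 0.0339/0.10 = 0.34.

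**What a bias below the half-width does.** It still shifts the interval. By exact binomial calculation at n = 300 and an assumed true 10%, the coverage of a 95% Wilson interval is 96% with nothing missed, 94% with 10% of cases missed, and 83% with 20% missed.

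**The case against.** The strongest reply is that the harm depends on a presentation the plan never commits to. Section 9.18.6 introduces its list as questionnaire topics, section 9.12 does not name sepsis among the percentages to be estimated, and section 9.20 plans simple frequencies and proportions. If results were reported item by item, each item's wording would show its own age range. This stands. A reader might infer that the plan promises a biased sepsis rate from birth; no section does, so the bias is conditional.

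A second reply is that little is lost. Pneumonia, suspected NEC, hospitalization for any reason and cause of death have no age floor, diagnoses of admitted infants are taken from charts (section 9.16), and the form itself is not in the documents and may record more. A reader might infer that first-week illness goes unrecorded; that is not supported. What is missing is a rule that counts it as sepsis.

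A third reply concerns the benchmark and the remedy. First-week clinical signs are less specific, so counting them could trade an undercount for false positives. The IMCI signs are not listed in the documents, so whether the existing 7 to 59 day item could simply be started at birth cannot be checked here. Both points stand. They are why the first-week cases need their own row, and why the choice of signs belongs to the investigators.

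Finally, a reader might infer that deaths between 72 hours and day 7 could be classified from records alone. Section 9.16 also has the mother questioned at sick visits and admissions, and section 9.11 provides for verbal autopsy in Tanzania.

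**Conclusion.** The gap is certain as a matter of wording: under the listed items, an episode on days 0 to 6 without a positive culture that ends before day 7 is not classified as sepsis. The plan gives no reason, although it observes those days and expects undetected early sepsis among enrolled infants. Any sepsis percentage read as covering follow-up from birth would be understated relative to clinical-or-culture sepsis.

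The size cannot be derived from the documents. On the assumed values above, the shortfall runs from 0.5 points (5%, f = 10%) to 5.0 points (10%, f = 50%). It stays within one site's sampling error unless f exceeds 49% at a true 5% or 34% at a true 10%. No hypothesis test is planned, so no test is affected. The change is worth making because it costs little and settles what the reported figure means, not because a large bias has been shown.

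**What to change.** For outcome classification only, with no change to care:

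1. Add a days 0 to 6 clinical severe-infection category to the sepsis outcome. The investigators choose the signs and first confirm that the form collects them for those days.
2. Ascertain it from the baseline and week-1 infant health questionnaires, the questions put to the mother at sick visits and admissions (section 9.16), and facility records.
3. Report four separate rows: days 0 to 6 clinical, 7 to 59 days clinical, 60 days or older, and culture-confirmed. Do not pool the first-week clinical row with the others without noting its lower specificity.
4. State that ascertainment for deaths between 72 hours and day 7 may be incomplete. Such infants can miss the week-1 questionnaire and then depend on sick-visit or inpatient data, records, or verbal autopsy, which is assured only in Tanzania.

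If the form does not support this, label the clinical sepsis percentage as starting at day 7 and show first-week culture-confirmed cases separately.

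Cost: if the signs are already collected, one definition, some table rows and two limitation sentences. If not, either a change to the baseline and week-1 form or the label-only version, which needs no new data. Neither requires a new visit or test.

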9.14 Schedule of data collection

We will collect a variety of information from the mother-infant pairs enrolled in the prospective and extension cohort throughout the study, as shown in Table 7. Table 7.1 shows the data collection time for the prospective cohort 6-month extension. The additional phone check-ins (are around 7.5 and 10.5 months) are only applicable for Tanzania and/or Malawi.

Table 7: Data collection schedule for prospective cohort

Weeks and months of infant's life	Baseline	Weekly for first 6 weeks				Monthly				
		0	1	2	4	6	2	3	4	6
Demographics and pregnancy history	✓	✓								
Gestational age	✓									
Infant anthropometrics	✓	✓	✓	✓	✓	✓	✓	✓	✓	
Maternal anthropometrics	✓				✓					✓

Infant feeding/maternal lactation questionnaire	✓	✓	✓	✓	✓	✓	✓	✓	✓
Infant health questionnaire	✓	✓	✓	✓	✓	✓	✓	✓	✓
Maternal health questionnaire	✓	✓	✓	✓	✓	✓	✓	✓	✓
Home Water/Sanitation Assessment						As required			
Sick visit or inpatient data						As required			
Mortality						As required			

Table 7.1: Data collection schedule for prospective cohort extension

Months of infant's life	Monthly			
	7.5	9	10.5	12
Demographics and home environment		✓		✓
Well-being		✓		✓
Infant anthropometrics		✓		✓
Maternal anthropometrics				✓
Infant feeding/maternal lactation	✓	✓	✓	✓
Infant health	✓	✓	✓	✓
Maternal health	✓	✓	✓	✓
Home Water/Sanitation Assessment		✓		✓
Mortality	✓	✓	✓	✓

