 - (1) confirmed NEC – modified Bell’s stage II or greater with pneumatoisis or portal venous gas on abdominal x-ray as well as intestinal (abdominal distention, blood in stool, abdominal tenderness) and clinical features (temperature instability, apnea, bradycardia, lethargy, metabolic acidosis, thrombocytopenia). (Kliegman and Walsh 1987)
 - (2) suspected NEC – two of the following: abdominal distention, blood in stool, systemic features of lethargy/apnea/hypotonia. (Quigley 2018)
- *Seizures, neonatal encephalopathy* (based on clinical records)
- *Hyperbilirubinemia/Kernicterus* (based on clinical records)
- *HIV diagnosis*: A subset of children whose mothers’ test negative in prenatal testing may have subsequent exposure due to maternal peripartum HIV infection. We anticipate that these children will be at higher nutritional risk. Additionally, some percentage of children who are HIV exposed will seroconvert during the six-month follow up period. We will encourage testing of all children who do not grow adequately for HIV and will also encourage testing of all children with known HIV exposure at intervals per the country standard of care.
- *Hospitalization*: composite hospitalization for any reason. Clinic stay duration and discharge timing will be captured as well as supplementary feeds (e.g. nasogastric feedings, fortified feedings).
- *Malnutrition*: Severe acute malnutrition (SAM)/ moderate acute malnutrition (MAM)

Infant mortality (asked at all data collection time points, including follow up phone calls)

- Date and time of death
- Cause of death, if available via medical record, or verbal autopsy in Dar es Salaam.

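### The suspected NEC definition has no age window and does not exclude infectious diarrhoea, so bloody diarrhoea with lethargy or distension later in infancy would be counted as suspected NEC

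*Combined protocol and SAP*

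**What the plan says.** Section 9.18.6 (Infant health questionnaire) gives NEC two categories. Confirmed NEC needs modified Bell's stage II or greater, with specified findings on abdominal x-ray plus intestinal and clinical features. Suspected NEC needs only "two of the following: abdominal distention, blood in stool, systemic features of lethargy/apnea/hypotonia". No age, gestational-age or in-hospital restriction is attached to the suspected category, and nothing excludes infectious diarrhoea.

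Two neighbouring entries do carry an age range. Possible serious bacterial infection is "evidence of severe clinical illness in an infant aged 7-59 days per IMCI criteria", and very severe febrile illness is "Fever + danger signs in a child 60 days or older per IMCI criteria". The diarrhoea entry lists persistent, acute, severe (with dehydration) and hospitalised diarrhoea. It has no bloody-stool category and no rule for an episode that also meets the NEC signs.

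Section 9.14 schedules the infant health questionnaire at every visit from baseline to 6 months (Table 7). Infant health is then collected at 7.5, 9, 10.5 and 12 months (Table 7.1); the 7.5- and 10.5-month contacts are phone calls in Tanzania and/or Malawi only. Section 9.12 says the main results are point estimates and confidence intervals for rates, including the proportion of infants who develop given conditions. Section 9.20 adds an assessment of morbidities over time for the full 0 to 12 months.

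**The concern.** The three signs are not specific to NEC. Two of them together describe a bowel emergency in a small newborn, but in an older infant they can equally describe bloody diarrhoea in a sick child. The background (Section 3) itself calls the complementary feeding period a time of increased diarrhoea and other gastrointestinal illness. A definition without an age window therefore lets a different illness into the suspected NEC count, and does so more as follow-up lengthens.

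At stake is how the descriptive rate is read. NEC appears in Section 3 in weighing donor milk against formula, so a site's suspected NEC proportion is likely to be looked at in that light. A larger sample would not remove the error, because it comes from the definition and not from sampling.

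**Working it through.** **1. The plan's own precision figure.** Section 9.12 gives ±2.7% for a true proportion of 5% with 250 infants. The Wald margin is 1.96 × √(0.05 × 0.95 / 250) = 0.0270, so the interval is 2.3% to 7.7%. The figure reproduces. It is a general example; the documents give no figure specific to NEC.

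**2. What the rule admits.** Treat lethargy/apnea/hypotonia as one sign, as the wording suggests. Three yes/no signs give 2³ = 8 combinations. Those with at least two signs number 3 + 1 = 4:

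- blood in stool + systemic features
- blood in stool + distension
- distension + systemic features
- all three

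Age does not enter the rule, so the same four qualify at two weeks and at nine months. Bloody diarrhoea with lethargy, or with distension, qualifies at either age. Such an episode would also be counted as acute diarrhoea, since the two entries are not mutually exclusive.

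**3. What the rule cannot touch.** Confirmed NEC needs x-ray evidence, so these signs alone never reach that category.

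**4. Illustrative size.** The documents give neither a suspected NEC rate nor a rate of later qualifying episodes, so both are assumptions. Let *s* be the proportion with suspected NEC as intended, and *d* the proportion with at least one later episode that meets the signs. If the two are independent:

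observed = 1 − (1 − *s*)(1 − *d*), and rise = *d*(1 − *s*).

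With 300 infants at a site, the last column is the rise divided by the 95% margin 1.96 × √(obs × (1 − obs) / 300):

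| *s* | *d* | Observed | Rise (points) | Infants, intended → counted | Rise ÷ margin |
|---|---|---|---|---|---|
| 1% | 1% | 1.99% | 0.99 | 3.0 → 6.0 | 0.63 |
| 1% | 3% | 3.97% | 2.97 | 3.0 → 11.9 | 1.34 |
| 3% | 1% | 3.97% | 0.97 | 9.0 → 11.9 | 0.44 |
| 3% | 3% | 5.91% | 2.91 | 9.0 → 17.7 | 1.09 |

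The rise is close to *d* itself whatever *s* is: about 1-3 points for *d* of 1-3%. That is roughly 0.4 to 1.3 times the sampling margin.

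**The case against.** The other side has several good arguments.

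- **Confirmed and suspected NEC are already separate.** This stands. No section says that they will be added together. Where Section 9.12 lists NEC among outcomes of interest, it means proven NEC, which this gap does not affect.
- **Maternal report alone may not suffice.** The source line for NEC, "Definitions (based on clinic records and maternal report", could mean that both are needed; malaria and culture results in the same list are worded as alternatives. The general description of the questionnaire, "self-report from mother/caregiver), and clinical records (when available", points the other way. The question is open, and the point does not rest on it.
- **The extension tool is not shown.** Section 9.16 refers to a revised follow-up tool, and Section 9.18.8 says the phone contacts ask mainly about status and feeding. The HIV entry in the morbidity list still speaks of six-month follow-up, which suggests that the list was written for the original cohort. It is therefore not certain that the NEC signs are asked after 6 months. However, no text drops NEC from the extension, and the gap exists in any case between the newborn period and 6 months.
- **Lack of an age range is common in this list.** Diarrhoea, pneumonia and malaria have none, and a positive culture counts at any age. This is fair, and the omission is not an internal contradiction. But those conditions keep their meaning through infancy, whereas a two-of-three sign rule for NEC does not.
- **The size is assumed.** This is correct, and it is stated as such.

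**Conclusion.** The point holds for suspected NEC only and is minor. Applied as written, the definition counts bloody diarrhoea with lethargy or distension at any age as suspected NEC. If 1-3% of infants had such an episode, which is an assumption, the suspected NEC proportion would rise by about 1-3 percentage points. The documents cannot narrow that range.

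A reader might go further and infer that the NEC rate as a whole would be inflated two- to four-fold, for example from 3 of 300 to (3 + 3)/300 = 2% or (3 + 9)/300 = 4%. The documents do not support this. Both inputs are assumed, and the sum joins categories that the plan keeps apart. A reader might also infer that the error falls more heavily on infants given other feeds and so distorts feeding comparisons. That is plausible, but the documents give no figure for it.

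**What to change.** In Section 9.18.6, add an age window to the suspected NEC definition, set by the clinical team before analysis. In Section 9.20, add that:

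- suspected NEC is tabulated by age at episode;
- it is never summed with confirmed NEC into one NEC rate;
- later episodes that meet the sign rule are reported on a separate line, and counted as diarrhoeal disease only when diarrhoea is recorded.

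The last condition matters. Moving every later episode into diarrhoeal disease would create a new error, because distension with lethargy and no diarrhoea fits none of the listed diarrhoea categories.

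The cost is a phrase in the definition and a few lines in the analysis section. No new data stream is needed, since the visit schedule already places each report at a known age. The downside is that a rare late case would be counted as NEC only if confirmed; the separate line keeps such episodes visible.
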